6.2.5 Concomitant Medication and Treatment

Concomitant medications include any prescription or over-the-counter preparation, including vitamins, dietary supplements, over-the-counter medications, and oral herbal preparations taken during the study. Patients may continue their baseline medication(s). Any diagnostic, therapeutic, or surgical procedure performed during the study period should be recorded, including the dates, description of the procedure(s), and any clinical findings, if applicable.

Permitted Concomitant Medication

Patients will receive concomitant medications to treat symptoms, AEs, and intercurrent illnesses that are medically necessary as part of standard care. Medications to treat concomitant diseases like diabetes, hypertension, etc., are allowed.

Restrictions and Prohibited Medications

Concurrent

Therapies: Concurrent therapy with any approved or investigative anticancer therapeutic outside of those included in this study is not allowed. Use of any immunosuppressive agents during the study must be confirmed by the sponsor-investigator.

Alcohol: Ethanol should be avoided on selinexor dosing days as it may compete for glutathione (GSH)-mediated metabolism.

Diet: There are no dietary restrictions on this study. Patients on selinexor should maintain adequate caloric and fluid intake.

Medications:

Patients should not take glutathione (GSH)-, S-adenosylmethionine (SAM)-, or N-acetylcysteine (NAC)-containing products during their participation in this study as these products may enhance the metabolism of selinexor. However, they are permitted if the patient has elevated liver function tests

Given the theoretical potential for GSH depletion, the total dose of acetaminophen should be ≤1 gram per day on days of selinexor dosing.

6.2.6 Use of Blood Products

During treatment, patients may receive red blood cell (RBC) or platelet transfusions, if clinically indicated, per institutional guidelines.

Appropriate anti-coagulation is allowed during the study (e.g., low molecular weight heparin, direct factor Xa inhibitors, etc.). Warfarin is allowed during the study provided patients are monitored for INR twice a week during the first two cycles of therapy, then weekly to biweekly thereafter.

Patients may receive supportive care with erythropoietin, darbepoetin, granulocyte-colony stimulating factor or granulocyte macrophage-colony stimulating factor, pegylated growth factors, and platelet stimulatory factors, in accordance with clinical practice or institutional guidelines prior to entry and throughout the study.

6.2.7 Contraception Requirements

Patients should not become pregnant or father a child while on this study because the study treatments in this study can affect an unborn baby. Women should not breastfeed a baby while on this study. It is important that patients understand the need to use birth control while on this study. Female patients of childbearing potential must agree to use two methods of contraception (one highly effective and one effective) and have a negative serum pregnancy test at Screening, and male patients must use an effective barrier method of contraception if sexually active with a female of childbearing potential.

Highly effective methods include:

Hormonal contraceptives (e.g., combined oral contraceptives, patch, vaginal ring, injectables, and implants)

Intrauterine device or intrauterine system

Vasectomy or tubal ligation

Effective methods include:

Barrier methods of contraception (e.g., male condom, female condom, cervical cap, diaphragm, contraceptive sponge)

Notes:

- *No barrier method by itself achieves a highly effective standard of contraception*
- *The proper use of diaphragm or cervical cap includes use of spermicide and is considered one barrier method.*
- *The cervical cap and contraceptive sponge are less effective in parous women.*
- *The use of spermicide alone is not considered a suitable barrier method for contraception.*
- *When used consistently and correctly, “double barrier” methods of contraception (e.g., male condom with diaphragm, male condom with cervical cap) can be used as an effective alternative to the highly effective contraception methods described above.*
- *Male and female condoms should not be used together as they can tear or become damaged.*

Alternatively, the following fulfill the contraception requirements:

A sexual partner who is surgically sterilized or post-menopausal.

Total (true) abstinence (when this is in line with the preferred and usual lifestyle of the patient), is an acceptable method of contraception. NOTE: Periodic abstinence (e.g., calendar, ovulation, symptothermal, post-ovulation methods) and withdrawal are not acceptable methods of contraception.

The method of acceptable contraception must be explained to both male and female potential patients. In order to be eligible for the study, patients must agree to use the methods of birth control described above throughout the study and for 3 months following the last dose of study treatment at the time of consent for the study.

Please see Section 7.12.1 for additional safety information related to pregnancy.

6.2.8 Radiation Treatment

If clinically indicated, palliative radiation therapy to non-target lesions is permitted but study treatment should be held for ≥ 1 day before the start of palliative radiation therapy and ≥ 1 day following each dose of palliative radiation therapy. Treatment with selinexor shall not be discontinued solely due to palliative radiation.

7 Assessment of Safety

7.1 Adverse Events

7.1.1 Definitions

Adverse event (AE): Any untoward medical occurrence in a patient or clinical investigation subject administered a pharmaceutical product and which does not necessarily have to have a causal relationship with this treatment. An AE can therefore be any unfavorable and unintended sign (including an abnormal laboratory finding, for example), symptom, or disease temporally associated with the use of study treatment, whether or not considered related to the study treatment.

7.1.2 Recording of Adverse Events

All AEs that begin or worsen after the patient has provided informed consent should be recorded by the Investigator, regardless of relationship to study treatment. AE monitoring should be continued for at least 30 days following the last dose of study treatment (i.e., through 30 days following last dose or until resolution or through the end of the study for events considered related to study treatment by the Investigator). AEs (including laboratory abnormalities that constitute AEs) should be described using a diagnosis whenever possible, rather than individual underlying signs and symptoms. When a clear diagnosis cannot be identified, each sign or symptom should be recorded as a separate AE.

The Investigator should ask the patient non-leading questions to determine if AEs occur during the study. AEs may also be recorded when they are volunteered by the patient, or through physical examination, laboratory tests, or other clinical assessments.

An AE should be followed until its resolution or until it is judged to be permanent, and assessment should be made at each visit (or more frequently, if necessary) of any changes in severity of the event, the suspected relationship to the study treatment, the interventions required to treat the event, and the outcome.

7.2 LABORATORY TEST ABNORMALITIES

Laboratory abnormalities that constitute an AE in their own right (i.e., are considered to be clinically significant, induce clinical signs or symptoms, require concomitant therapy, or require changes in study treatment), should be recorded as an AE. Whenever possible, a diagnosis rather than a symptom should be recorded (e.g., anemia instead of low hemoglobin). Laboratory abnormalities that meet the criteria for an AE should be followed until they have returned to normal or an adequate explanation of the abnormality is identified. When an abnormal laboratory or test result corresponds to a sign/symptom of an already reported AE, it is not necessary to separately record the laboratory/test result as an additional event.

A laboratory abnormality that does not meet the definition of an AE should not be recorded as an AE. A laboratory abnormality that results in a dose being held or modified would, by definition, be an AE. A Grade 3 or 4 event (severity per the current version of NCI CTCAE) does not automatically indicate an SAE unless it meets the definition of serious as defined in Section 1.1.1 and/or as per the Investigator's discretion.

7.3 ADVERSE EVENTS OF SPECIAL INTEREST (AESI)

AESIs for selinexor include cataracts and acute cerebellar syndrome. All cases of cerebellar toxicity, Grade 3 or higher must be reported (see Section 7.8).

7.4 Adverse Event Severity Assessments

The severity* of the AE should be graded by the Investigator according to the NCI CTCAE Grading Scale, utilizing NCI CTCAE (version 4.03: June 14, 2010). NCI CTCAE files can be accessed online at the following URL: <http://evs.nci.nih.gov/ftp1/CTCAE/About.html>.

If NCI CTCAE grading does not exist for an AE, the severity should be characterized as 'mild,' 'moderate,' 'severe,' 'life-threatening,' or 'fatal' (corresponding to Grades 1 to 5) according to the following definitions:

- Mild events are usually transient and do not interfere with the patient's daily activities.
- Moderate events introduce a low level of inconvenience or concern to the patient and may interfere with daily activities.
- Severe events interrupt the patient's usual daily activities.
- Life-threatening
- Fatal event.

*Severity is not the same as Seriousness: The term 'severe' is used to describe the intensity of an AE; the event itself could be of relatively minor clinical significance (e.g., 'severe' headache). This is not the same as a 'serious' AE. Grades do not define seriousness.

7.5 Adverse Event Causality

The Investigator will make a judgment regarding the relationship of the AE to study treatment, as outlined in Table 7.

7.6 Table 7: Classification of Adverse Events by Causality

Not related: The lack of a temporal relationship of the event to the study treatment makes a causal relationship not reasonably possible, or other drugs, therapeutic interventions, or underlying conditions provide a sufficient explanation.

Related: The temporal relationship of the event to the study treatment makes a definitive relationship, and the event is more likely explained by exposure to the study treatment than by any other drugs, therapeutic interventions, or underlying conditions.

7.7 Adverse Event Reporting

The Investigator will report all AEs (including all non-serious AEs) to Karyopharm Pharmacovigilance every 6 months in the form of line-listings. The line listings will include the following information: subject number, study drug information (start/stop date, dosage, and frequency), adverse event (onset/stop date, event intensity, event outcome and action taken), seriousness (serious with applicable criteria, or non-serious), and the Investigator's causality assessment. Karyopharm Therapeutics will provide the preferred template.

7.8 Serious Adverse Events

An AE is considered an SAE if at least one of the following conditions applies:

- Death was an outcome of an adverse event;
- Life threatening AE (i.e., an event in which the patient was at risk of death at the time of the event; it does not refer to an event that hypothetically might have caused death if it were more severe);
- Requires inpatient hospitalization or prolongation of existing hospitalization;

- Emergency room visits that do not result in admission to the hospital should be evaluated for one of the other serious outcomes (e.g., life-threatening; required intervention to prevent permanent impairment or damage; other serious medically important event);
- Results in persistent or significant disability/incapacity;
- Is a congenital anomaly/birth defect;
- A new cancer diagnosed during the study (histopathologically different from the cancer under study; and
- Any important medical events that may not result in death, are not life-threatening, or do not require hospitalization may be considered SAEs when, based on appropriate medical judgment, they may jeopardize the patient and may require medical or surgical intervention to prevent 1 of the outcomes listed in this definition. Examples of such events include allergic bronchospasm requiring intensive treatment in an emergency room or at home, blood dyscrasias or convulsions that do not result in in-patient hospitalization, or the development of drug dependency or drug abuse.

Hospitalizations for elective surgery or other medical procedures that are not due to an AE are not considered SAEs. A hospitalization meeting the regulatory definition for 'serious' is any inpatient hospital admission that includes a minimum of an overnight stay in a health care facility. An emergency room visit is not considered a hospitalization unless it results in an official admission to the hospital.

Progression of the malignancy (including fatal outcomes) should not be reported as an SAE during the study or within the safety reporting period (see Section 6.9.2.2). Sudden and unexplained death should be reported as an SAE. If there is any uncertainty about a finding being due solely to progression of malignancy, the finding should be reported as an AE or SAE, as appropriate.

7.9 Recording of Serious Adverse Events

Per the Good Clinical Practices, it is recommended that Investigator has the responsibility to record and document all SAEs occurring from the signing of the Informed Consent Form until at least 30 days after the patient has stopped study treatment.

7.10 Reporting of Serious Adverse Events

Every SAE, regardless of the causal relationship to the Karyopharm medications, occurring after the patient has signed informed consent until 30 days after the patient has stopped study treatment must be reported to the Karyopharm Pharmacovigilance within 24 hours of awareness. Karyopharm Therapeutics, Inc. will provide the required SAE Report Form.. For reporting any SAE to Karyopharm Pharmacovigilance Department, a completed and signed (by the Investigator) SAE Report Form will be submitted to Karyopharm Pharmacovigilance:

Completed and signed SAE report forms must be emailed to:

Pharmacovigilance Department

Karyopharm Therapeutics Inc.

Email: [contact]

Any SAE observed after the 30-day follow-up period should only be reported to Karyopharm if the Investigator suspects that the SAE has causal relationship to study treatment.

An SAE should be followed until its resolution or until it is judged to be permanent, and assessment should be made at each visit (or more frequently, if necessary) of any changes in severity of the event, the suspected relationship to the study treatment, the interventions required to treat the event, and the outcome. New information, recurrences, complications, or progression of the initial SAE must be reported as follow-up to the initial report within 24 hours of the Investigator receiving the follow-up information.

Investigators are responsible as applicable for notifying their appropriate Health Authorities, Institutional Review Board or Local and Central Ethics Committees (EC) of all SAEs in accordance with local regulations.

Karyopharm Therapeutics will report applicable SAEs to other applicable Regulatory Agencies and Investigators utilizing the Karyopharm product, as may be required.

7.11 Suspected Unexpected Serious Adverse Reactions

Suspected unexpected serious adverse reactions (SUSARs) are SAEs that are unexpected (per the current version of the IB) and judged by the Investigator or Karyopharm to be related to the study treatment administered.

SUSARs will be collected and reported to the competent authorities and relevant ethics committees in accordance with the FDA's 'Safety Reporting Requirements for Investigational New Drugs and Bioanalytical/Bioequivalence Studies' or as per national regulatory requirements in participating countries.

7.12 Procedures for Handling Special Situations

7.12.1 Pregnancy

Note: Pregnancy per se is not considered to be an AE; however, it is discussed here because of the importance of reporting pregnancies that occur during studies and because a medical occurrence observed in the mother or fetus/newborn would be classified as an AE.

To ensure patient safety, a pregnancy occurring while the patient is on study treatment must be reported to Karyopharm Pharmacovigilance by email or fax within 24 hours of first knowledge of its occurrence. A pregnancy report form is provided by Karyopharm Therapeutics Inc.

The pregnancy should be followed up to determine outcome, including spontaneous or voluntary termination, details of the birth, and the presence or absence of any birth defects, congenital abnormalities, or maternal and/or newborn complications.

A pregnancy in a female partner of a male patient must be reported to Karyopharm Pharmacovigilance within 24 hours of learning of its occurrence.

Pregnancies must be reported to Karyopharm Pharmacovigilance, regardless of whether the patient withdraws from the study or the study is completed, for 3 months after the patient receives his/her last dose of study treatment. Patients should be instructed to inform the investigator regarding any pregnancies.

Any SAE that occurs during pregnancy must be recorded on the SAE report form (e.g., maternal serious complications, therapeutic abortion, ectopic pregnancy, stillbirth, neonatal death, congenital anomaly, birth defect) and reported within 24 hours in accordance with the procedure for reporting SAEs.

7.12.2 Abuse, Misuse, Medication Errors, Overdose, and Occupational Exposure

All incidences of abuse, misuse, medication errors, overdose, and occupational exposure are required to be reported to Karyopharm pharmacovigilance on an SAE report form emailed to [contact], regardless of whether or not there is an associated AE or SAE.

7.13 OVERDOSE

An overdose is a deliberate or accidental administration of any Karyopharm treatment to a study patient, at a dose greater than that which was assigned to that patient per the study protocol. If an overdose occurs, Karyopharm Pharmacovigilance should be notified immediately, and the patient should be observed closely for AEs. Resulting symptoms should be treated, as appropriate, and the incident of overdose and related AEs and/or treatment should be recorded. Overdose is to be reported on an SAE report form to Karyopharm pharmacovigilance regardless of whether or not an AE or SAE has occurred due to the overdose. If the overdose is associated with an SAE, the SAE report form must be submitted to Karyopharm pharmacovigilance within 24 hours of awareness. If there is no AE or SAE, the report must be submitted as soon as possible.

7.14 ABUSE, MISUSE, OR MEDICATION ERROR

Abuse is the persistent or sporadic, intentional excessive use of the study drug which is accompanied by harmful physical or psychological effects.

A medication error is any preventable incident that may cause or lead to inappropriate medication use or patient harm while the medication is in the control of the health care professionals or patients. Such incident may be due to health care professional practice, product labeling, packaging and preparation, procedures for administration, and systems, including prescribing; order communication; and nomenclature; compounding; dispensing; distribution; administration; education; monitoring; and use.'

All occurrences of abuse, misuse or medication error with Karyopharm drug are to be reported on an SAE report form to Karyopharm pharmacovigilance regardless of whether or not an AE or SAE has occurred due to the abuse, misuse or medication error. If the abuse, misuse or medication error is associated with an SAE, the SAE report form must be submitted to Karyopharm pharmacovigilance within 24 hours of awareness. If there is no AE or SAE, the report must be submitted as soon as possible.

7.15 OCCUPATIONAL EXPOSURE

Occupational exposure is the exposure to a study drug as a result of one's professional or non-professional occupation.

All occurrences of occupational exposure with Karyopharm drug are to be reported on an SAE report form to Karyopharm pharmacovigilance regardless of whether or not an AE or SAE has occurred due to the occupational exposure. If the occupational exposure is associated with an SAE, the SAE report form must be submitted to Karyopharm pharmacovigilance within 24 hours of awareness. If there is no AE or SAE, the report must be submitted as soon as possible.

8 Statistical Considerations

8.1 Trial Design

This is a non-randomised, open label two armed phase II trial. Arm A includes patients with thymoma and arm B include patients with thymic carcinoma.

The primary objective of the trial is to determine the effect of selinexor in patients with inoperable thymoma and in patients with thymic carcinomas, previously treated with with at least one platinum containing chemotherapy regimen as determined by overall response rate according to RECIST 1.1.

The study is composed of two similar phase II trials conducted in the US and Europe. The final analysis will be performed on data pooled from both trials. The calculation of the total sample size is based on the pooling of data from both trials.

The following assumptions are the basis for the sample size:

- Simon's minimax design will be used
- A response rate of 10 % is considered clinical irrelevant.
- A response rate of 30 % is considered undesirable to overlook.
- Type one error rate: 0.05
- Power: 0.80
- Stage 1: 15 evaluable patients in each arm
- Stage 2: 10 evaluable patients in each arm
- For each arm: If response is observed in 2/15 patients in stage 1, accrual will continue in stage 2.
- For each arm: If response in 5 out of 25 patients, the alternative hypothesis is accepted and the drug is considered active and appropriate for further evaluation.

Included patients who are not evaluable for response will be replaced.

All patients receiving at least one dose of selinexor will be included in the final analysis of primary and secondary endpoints. However this is not an intention to treat (ITT) study.

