Sample size calculation	
Simon's minimax design will be used. The following assumptions are used in each of the two arms:
 
 • A response rate of 10 % is considered clinically irrelevant • A response rate of 30 % is considered promising and clinically relevant • Type one error rate: 0.05 • Power: 0.80 
In stage 1, 15 evaluable patients are to be included. If response according to RECIST 1.1 and/or ITMIG criteria is observed in 2/15 patients in stage 1, accrual of 10 evaluable patients will continue in stage 2. If responses are observed in 5 out of 25 patients, the alternative hypothesis is accepted and Selinexor is considered active and appropriate for further evaluation. This is not an intention to treat (ITT) study and included patients who are not evaluable for response will be replaced.

Planned interim analysis	An interim analysis is planned after stage 1. Decision to go to stage 2 will be made by a consortium with representatives from both EU study and US study and Karyopharm. In case 2 patients out of 15 patients derive clear clinical benefit according to a unanimous agreement among members of the consortium, a decision can be made to proceed to stage 2. Clear clinical benefit is defined as: non-progressive disease with improvement in tumor related symptoms and treatment is well tolerated.

FLOW CHART: SCHEDULE OF ASSESSMENTS DURING THE STUDY

	Screening		Cycle 1- 2	Cycle ≥ 3	EOT Visit	EOS Visit
Visit window [days]	< 28 days prior to start of therapy	< 7 days prior to start of therapy	Day 1 & 15 ± 3 days	Day 1 ± 3 days	Off treatment	30 days ± 7 days
Informed consent ¹	x					
Inclusion and exclusion criteria		x				
Demographics	x					
Medical History ²	x					
Pregnancy test (if applicable) ³		x			x	
Body height and weight ⁴		x	x	x	x	x
Vital signs ⁵		x	x	x	x	x
Physical examination and ECOG ⁶	x		x	x	x	x
12-lead ECG	x					
Hematology (CBC) ^{7,8}		x	x	x	x	x
Complete Serum chemistry ^{7,9}		x	x		x	x
Limited Serum chemistry ¹⁰				x		
Assessment of disease status ¹²	x			x	x	
Selinexor Dispensing			x ¹⁶	x		
Adverse events	x	x	x	x	x	x
Concomitant Medication	x	x	x	x	x	x
Obtain Archive Tumour biopsy tissue ¹³		x				
Ophthalmic exam ¹⁴	x					
Nutritional consultation ¹⁵	x					

Notes

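### The final success rule of 5/25 is one response too low for the named Simon minimax design: its one-sided type I error is 9.3%, not the stated 5%

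*Combined protocol and SAP*

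**What the plan says.** Section 8.1 (Trial Design) gives the design as follows:

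- Family: "Simon's minimax design will be used".
- Null rate: "A response rate of 10 % is considered clinical irrelevant". Alternative rate: "A response rate of 30 % is considered undesirable to overlook".
- Error: "Type one error rate: 0.05", with power 0.80.
- Size: "Stage 1: 15 evaluable patients in each arm" and "Stage 2: 10 evaluable patients in each arm", so 25 per arm.
- Stage 1: accrual continues on 2 responses in 15.
- Final decision: "For each arm: If response in 5 out of 25 patients, the alternative hypothesis is accepted and the drug is considered active".

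The synopsis, under Sample size calculation, repeats the final rule: "If responses are observed in 5 out of 25 patients, the alternative hypothesis is accepted and Selinexor is considered active". Neither place says more than 5 or names 6, and neither accepts a type I error above 0.05.

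Section 8.1.1 reports the interim result. The thymoma cohort had 3 responses in 15 by the ITMIG criteria and 2 by RECIST, and it continues with 10 more patients. The thymic carcinoma cohort had none and is closed.

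**The concern.** A Simon design is usually tabulated by its rejection limits: stop if r1 or fewer respond in stage 1, and reject the drug if r or fewer respond in total. A protocol that states success counts must add one to each limit. Here the stage 1 count of 2 fits a limit of r1 = 1 with one added. The final count of 5 looks like the limit itself with nothing added, so the two stages appear to follow different conventions.

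If so, 5 responses in 25 is a negative result under the named design, yet the text would call the drug active and suitable for further evaluation. Section 8.2.3 plans only a response rate with a 95% confidence interval, so this count is the only formal decision rule for efficacy. The stated error rate and the written rule could not both be true.

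**Working it through.** **Inputs** (Section 8.1, repeated in the synopsis): p0 = 0.10, p1 = 0.30, n1 = 15, n2 = 10, n = 25, continue at 2 or more of 15, success at 5 or more of 25. Sidedness is not stated, but a Simon design is one-sided by construction. The calculation assumes a binding stage 1 rule and one response criterion at both stages. RECIST 1.1 is used because it defines the primary endpoint.

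**Step 1: reproduce the design.** An exhaustive search over stage sizes and limits at alpha 0.05 and power 0.80 returns the minimax design n1 = 15, r1 = 1, n = 25, r = 5, with expected sample size 19.5 under the null. The protocol's 15 + 10 patients and its 2/15 rule reproduce exactly. Rejecting the drug at 5 or fewer means success at 6 or more. In the search, every 25-patient design meeting 0.05 and 0.80 has 6 as its success count.

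**Step 2: operating characteristics.** For success count c,

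P(success) = Σ over x = 2,…,15 of P(X1 = x) × P(X2 ≥ c − x), with X1 ~ Bin(15, p) and X2 ~ Bin(10, p).

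Type I error at p = 0.10:

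| Stage 1 responses | P(X1 = x) | c = 5: P(X2 ≥ 5 − x) | Product | c = 6: P(X2 ≥ 6 − x) | Product |
|---|---|---|---|---|---|
| 2 | 0.26690 | 0.07019 | 0.01873 | 0.01280 | 0.00341 |
| 3 | 0.12851 | 0.26390 | 0.03391 | 0.07019 | 0.00902 |
| 4 | 0.04284 | 0.65132 | 0.02790 | 0.26390 | 0.01130 |
| 5 | 0.01047 | 1 | 0.01047 | 0.65132 | 0.00682 |
| 6 or more | 0.00225 | 1 | 0.00225 | 1 | 0.00225 |
| **Sum** | | | **0.0933** | | **0.0328** |

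The same sum at p = 0.30 gives power 0.898 for c = 5 and 0.802 for c = 6. The difference in type I error, 0.0933 − 0.0328 = 0.0605, is the probability under the null of passing stage 1 and finishing with exactly 5 responses.

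**Step 3: does another reading rescue 5/25?**

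| Reading | Type I error | Power |
|---|---|---|
| Continue at 1 or more of 15, success at 5 or more | 0.0977 | 0.909 |
| Continue at 3 or more of 15, success at 5 or more | 0.0745 | 0.842 |
| No binding stage 1 stop, success at 5 or more | 0.0980 | 0.910 |
| Both counts read as "more than" (3 or more, then 6 or more) | 0.0294 | 0.770 |

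The first three exceed 0.05 and the fourth misses the stated power. A different intended alpha does not explain the rule either: the minimax size is 18 at alpha 0.10 and 29 at 0.025.

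**Step 4: where the thymoma cohort stands.** With 2 RECIST responses in 15, the written rule needs 3 more from 10 patients and the 6/25 rule needs 4.

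- At a true rate of 10%: P(X2 ≥ 3) = 0.0702 and P(X2 ≥ 4) = 0.0128.
- At a true rate of 30%: P(X2 ≥ 3) = 0.617 and P(X2 ≥ 4) = 0.350.

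**The case against.** The arithmetic is not open to dispute, but five points limit or qualify it.

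1. **The consequence is bounded.** The rule supports only a judgement that further evaluation is appropriate, only the thymoma cohort is still open, and the two cut-offs differ only if exactly 5 of 25 respond. All true. That count is nevertheless plausible, needing three more RECIST responses in ten patients, and the rule exists to settle such cases.
2. **The higher cut-off costs power.** Overall power falls from 0.898 to 0.802, and the conditional chance of success at a true 30% falls from 0.617 to 0.350. This stands as a real cost. The overall figure still meets the 0.80 that the plan states.
3. **9.3% is not the exact error of the trial as run.** The synopsis allows continuation on RECIST and/or ITMIG response, and both the synopsis and Section 8.1.1 allow it on agreed clear clinical benefit. These routes only loosen the gate. With RECIST counted at the end, the error under 5/25 can then reach at most 9.8%.
4. **The 5/25 sentence names no response criterion.** If ITMIG responses counted, the cohort would start from 3/15. The conditional false-positive chance would be 26.4% with 5/25 and 7.0% with 6/25. RECIST is the reasonable reading, but it is an assumption.
5. **The two-sided 95% interval does not separate the cut-offs.** It includes 10% at 5/25 (6.8% to 40.7%) and also at 6/25 (9.4% to 45.1%). That is correct, so the interval is no argument for 6. The one-sided 95% lower bound, which matches the design, is 8.2% at 5/25 and 11.0% at 6/25.

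**Conclusion.** The concern holds. The written rule has a one-sided type I error of 0.0933, almost twice the stated 0.05, and power 0.898. The named design requires 6 of 25, which gives 0.0328 and 0.802. No alternative stage 1 gate brings 5/25 below 0.0745. That the failure limit was copied as the success count is the likely explanation, but the documents do not say so.

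The figures assume 25 evaluable patients, RECIST response at both stages and a binding 2/15 gate. Relaxing the gate moves the error to at most 0.098 and does not alter the conclusion. This must be fixed, because the plan's only formal efficacy decision rule contradicts its stated error rate in a cohort that is still accruing.

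**What to change.** In Section 8.1 and in the synopsis (Sample size calculation), state that the drug is considered active only with 6 or more responses among 25 evaluable patients. Name RECIST 1.1 as the criterion counted. Make the same change in the parallel EU protocol, because stage decisions and the final analysis use pooled data.

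Make the amendment before stage 2 responses are reviewed, if that is still possible. The trial is open label and Section 9.2 has activity discussed in monthly US–EU calls, so the amendment should record which stage 2 responses were known when it was written. The change makes a positive claim harder to reach, so it cannot be read as favouring the drug.

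If the sponsor prefers to keep 5/25, both places should give type I error 0.093 and power 0.90, remove the 0.05 claim, and no longer present the rule as the minimax design for 0.05 and 0.80.

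The cost is a short amendment in two aligned protocols and no extra patients. With 6/25 the sponsor also gives up power above the planned level: 0.802 instead of 0.898 overall, and 0.350 instead of 0.617 from the current 2/15 if the true rate is 30%.
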